**5.5. Tertiary/Exploratory Endpoints Analysis****5.5.1. Definition of Endpoint****QOL-B NTM module**

The QOL-B respiratory symptom domain and NTM module will be assessed in this study. The respiratory symptom domain consists of 9 items. The NTM module is developed specifically for NTM symptoms and consists of NTM symptoms (7 items), body image (4 items), digestive symptoms (6 items), and eating problems (3 items). The NTM symptoms domain includes the following items: feverish (chills, sweating), sensitivity to smell, sensitivity to taste, memory problems, bad taste in mouth, bothered by cold weather, problems sleeping. Responses are measured using a 4-point Likert Scale (eg, “a lot”, “a moderate amount”, “a little”, or “not at all”). Individual domain scores are calculated, scaled from 0 to 100 (100=best HRQOL).

**5.5.2. Analysis Methods**

The following endpoints will be descriptively summarized and listed. No imputation rules will be applied for withdrawn and missing data.

- The domain scores of QOL-B NTM module and the changes from baseline at Weeks 24, 48, and 60.
- Rate of culture reversion (relapse or reinfection) in MIGIT up to Week 60. The denominator is defined as the number of subjects with sputum culture conversion before Week 60 and the numerator is defined as the number of subjects with at least one positive culture up to Week 60 after the culture conversion.
- Distribution of MICs to BDQ, RFP, RBT, EB, CAM, AMK and SM.
- Percentage of participants having MAC isolates with acquired resistance to CAM (MIC  $\geq 32$   $\mu\text{g/mL}$ ) detected by a phenotypic method up to Week 60.
- Percentage of participants having MAC isolates with increased MICs to BDQ (at least 4-fold increase) up to Week 60
- For participants who achieved sputum culture conversion, the changes from baseline in the total score of SGRQ, the domain scores of QOL-B NTM module, and chest CT findings

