Upon completion of the 48-week treatment period, the participants in Group A who achieved culture conversion will transfer to the follow-up period of 12 weeks. During the follow-up period, the converters will be treatment free for MAC-LD in order to confirm the durability of culture conversion. Non-converters at Week 48 in Group A will be discontinued from the study and switched to another treatment regimen if they continue chemotherapy because the duration of BDQ treatment is 48 weeks. On the other hand, the participants in Group B will continue the study intervention up to Week 60. Upon completion of the 60-week study intervention period, the study is completed, but the participant may continue SOC of local guidelines or medical practice at each study site for at least 1 year after culture conversion at the discretion of the investigators.

In addition, this study provides an option to receive BDQ-containing regimen (BDQ + CAM + EB) for non-converters in Group B at Week 24 as the optional cohort. The participants may continue Group B regimen, switch to an individualized treatment regimen, or BDQ-containing regimen in the optional cohort at the discretion of the investigators. The criteria for switching to optional cohort after Week 24 are detailed in Section 6.8.2. When the investigator changes to BDQ-containing regimen, 2-week washout of rifamycin is required before initiation of BDQ-containing regimen. The participants switching to BDQ-containing regimen will be considered treatment failures for rifamycin-containing regimen and will be followed up for efficacy and safety for BDQ-containing regimen.

In this optional cohort, during the 48-week treatment period (from Day 1 in optional cohort [OPD1] to Week 48 in optional cohort [OPW48]) of the study, participants may be changed to individualized treatment regimen. The investigators can postpone the decision to transfer to the optional cohort for up to Week 32 in order to confirm a sputum culture positive at Week 24, if necessary. Regardless of delay in the transition phase, the treatment duration of the optional cohort will be for 48 weeks.

All participants who switched to the optional cohort will be considered as treatment failure to rifamycin-containing regimen.

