The standard duration of administration with BDQ for the treatment of MDR-TB with a known bactericidal effect is 24 weeks, whereas the duration of administration with BDQ for MAC-LD, where a bacteriostatic effect is suggested, needs to be longer, and is therefore set at 48 weeks and drug free follow-up period for 3 months is planned to evaluate the recurrences after completion of treatment to evaluate appropriate treatment duration. On the other hand, the participants in Group B who achieved culture conversion at Week 24 will continue up to Week 60. This 60-week duration is consistent with the end of follow-up period in Group A. Upon completion of the 60-week study intervention period, the study is completed, but the participant may continue SOC of local guidelines in Japan, South Korea and Taiwan or medical practice at each study site for least 1 year after culture conversion at the discretion of the investigators after study completion.

In addition, participants who have not achieved culture conversion in Group A (BDQ-containing regimen) will continue their assigned regimen until Week 48, unless they have difficulty continuing due to failure to respond (see Section 6.8.1, based on non-conversion and clinical worsening) or the occurrence of AE related to the regimen. If participants were judged to have difficulty continuing due to failure to respond to the regimen or the occurrence of the regimen related AE, at the discretion of investigators, there will be options to discontinue from the study or switch to an individualized treatment regimen (in principle, add on injectable SM, injectable or inhalation suspension of AMK).

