##### **Time to sputum culture conversion in MGIT**

For this time-to-event analysis, an event is defined as sputum culture conversion in MGIT. The definition of sputum culture conversion is described in Section 5.3.1.

The date of event is defined as the date of the first of 3 consecutive negative sputum cultures taken at least 25 days apart. For subjects who achieve culture conversion after switching to individualized treatment regimen, the culture conversion after switching will not be treated as an event.

The rules of censoring are as follows.

Analysis period	Rules of censoring
From Day 1 to Week 24	
 
● If study discontinuation before event, date of censoring will be study discontinuation date.
 
● If no study discontinuation and no event, date of censoring will be the last sputum culture test date.
 

From Day 1 to Week 48	
 
● If switching to optional cohort before event, date of censoring will be the last sputum culture test date before switching to optional cohort.
 
● If study discontinuation before event, date of censoring will be study discontinuation date.
 
● If no switching to optional cohort and no study discontinuation and no event, date of censoring will be the last sputum culture test date.
 

From Optional Day 1 to Optional Week 48 (only for subjects who switched to Optional Cohort)	
 
● If study discontinuation before event, date of censoring will be study discontinuation date.
 
● If no study discontinuation and no event, date of censoring will be the last sputum culture test date.
 

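### The exploratory culture reversion rate counts unobserved converters as reversion-free and mixes on-drug with drug-free time, so it does not measure recurrence after treatment

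*SAP*

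**What the plan says.** SAP 5.5.2 defines the rate of culture reversion in MGIT up to Week 60 as a simple proportion. For the denominator: "The denominator is defined as the number of subjects with sputum culture conversion before Week 60". For the numerator: "the numerator is defined as the number of subjects with at least one positive culture up to Week 60 after the culture conversion". The same section adds: "No imputation rules will be applied for withdrawn and missing data". It sets no minimum number of later cultures and no censoring rule, and it does not split the result by treatment phase.

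The arms are handled differently after Week 48 (Protocol 4.1). For Group A converters: "During the follow-up period, the converters will be treatment free for MAC-LD in order to confirm the durability of culture conversion". For the others in that arm: "Non-converters at Week 48 in Group A will be discontinued from the study". In the control arm, "the participants in Group B will continue the study intervention up to Week 60". Protocol 4.2 states what the Group A period is for: "drug free follow-up period for 3 months is planned to evaluate the recurrences after completion of treatment", with a view to judging treatment duration.

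SAP 5.1 already defines a separate follow-up phase for Group A, and SAP 5.6.2 reports adverse events by phase. The reversion analysis does not use that split.

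**The concern.** A reversion can be seen only in a culture taken after conversion has been confirmed. Under the SAP rule, a converter who has none is not treated as unknown. That participant enters the denominator and can never enter the numerator. Declining to impute does not help, because the zero is built into the proportion.

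The second problem is what the number means. In Group A it combines positives that occur on bedaquiline, up to Week 48, with positives after dosing stops. In Group B every culture up to Week 60 is on drug. A reader who wants to know how often disease returns after a completed 48-week course cannot obtain that from the pooled figure, and no planned analysis isolates it. The treatment-duration question in Protocol 4.2 would then rest on a number that answers something else.

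**Working it through.** **Plan's own figure.** The documents give no figure for reversion. Their sample-size figure serves only to size the converter groups. For 10% v 30%, two-sided 5%, chi-square without continuity correction, the calculation returns 62 per arm with power 0.803. This agrees with Protocol 9.2. Expected Week 24 converters are 62 × 0.30 = 18.6 in Group A and 62 × 0.10 = 6.2 in Group B.

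**Step 1: cultures available after the confirming visit.** These are counted from the Schedule of Activities (every 4 weeks after Week 12).

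| Third negative at | Group A, on drug + drug-free | Group B, all on drug |
|---|---|---|
| Week 12 | 9 + 3 | 12 |
| Week 24 | 6 + 3 | 9 |
| Week 48 | 0 + 3 | 3 |
| Week 52 | not possible by design | 2 |
| Week 56 | not possible by design | 1 |

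A Group A converter who stays in the study has at least three later scheduled cultures. Drug-free cultures exist only in Group A.

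**Step 2: dilution by unobserved converters.** The SAP proportion equals the true risk among those observed × (1 − share with no later culture). Assume a true risk of 20%. With 10%, 20% or 30% unobserved, the SAP rate is 0.20 × 0.90 = 18%, 0.20 × 0.80 = 16%, or 0.20 × 0.70 = 14%. An at-risk denominator returns 20% each time. With 6.2 expected Week 24 converters in Group B, one unobserved person is 1/6.2, about 16% of that denominator.

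**Step 3: pooling in Group A.** Assumptions, none of them from the documents except the 30% (the planning rate):
- 30% of the arm is confirmed by Week 24, all taken as having 6 on-drug cultures left.
- A further 2 points are confirmed at each of the six visits from Week 28 to Week 48, leaving 5, 4, 3, 2, 1 and 0 on-drug cultures. The total is 42 points.
- There is no withdrawal.
- The risk of a positive per culture is q on drug and 5% off drug.

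Drug-free 12-week recurrence: 1 − 0.95³ = 14.3%.

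Share reaching Week 48 without a positive: S = [30(1−q)⁶ + 2 × Σ(1−q)ᵏ, k = 0 to 5] / 42.

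Pooled SAP rate: 1 − S × 0.95³. On-drug share of events: (1 − S) / pooled rate.

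| q on drug | S | Pooled rate | Events on drug |
|---|---|---|---|
| 1% | 0.951 | 18.5% | 26% |
| 2% | 0.905 | 22.4% | 43% |
| 3% | 0.860 | 26.3% | 53% |

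The pooled rate exceeds the drug-free risk in all three rows.

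**Step 4: comparison between arms.** Give both arms the same 2% risk at every culture, on and off drug. Group A's rate is then 14.9%. Group B starts with 10% confirmed by Week 24 (9 later cultures), plus x points at each of the nine visits from Week 28 to Week 60 (8 down to 0 later cultures):

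Group B rate = [10(1 − 0.98⁹) + x × Σ(1 − 0.98ᵏ), k = 0 to 8] / (10 + 9x) = (1.6625 + 0.6874x) / (10 + 9x).

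| Late Group B conversion, x | Group B | Group A |
|---|---|---|
| 0 | 16.6% | 14.9% |
| 0.2 | 15.3% | 14.9% |
| 0.5 | 13.8% | 14.9% |
| 1.0 | 12.4% | 14.9% |

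The order reverses between x = 0.25 and x = 0.3, so the sign of the imbalance depends on an input that the documents do not supply.

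**The case against.** The strongest defence is that the SAP implements the protocol's own endpoint, a reversion rate up to Week 60 among participants who had converted. Nothing labels that endpoint a post-treatment recurrence rate, and Protocol 4.2 does not assign the purpose of the drug-free period to it. This is correct, but it leaves that stated purpose without an analysis.

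Durability is also partly covered. SAP 5.4.2.2.2 compares a Week 60 composite between arms, SAP 5.4.2.2.3 summarises culture negativity by visit, and the reversion data are to be listed. None of these gives the proportion with a positive culture at Weeks 52-60 among those who entered follow-up.

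A reader might infer that the definition makes Group B look better at equal risk, because only Group B can convert late with few cultures left. The documents do not support that. Step 4 shows that the order depends on the rate of late conversion. Protocol 4.2.1 calls conversion beyond 24 weeks on standard therapy unlikely, and Protocol 6.8.2 lets Group B non-converters move to the optional cohort, which shrinks the pool of late converters.

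A related inference is that a Group B participant negative at Weeks 52, 56 and 60 enters the denominator with no later culture. That needs conversion to be dated at the first negative. SAP 5.4.2.1 says so for the time-to-event endpoint ("The date of event is defined as the date of the first of 3 consecutive negative sputum cultures taken at least 25 days apart"), but SAP 5.5.2 does not say which date applies to reversion. If conversion must be complete before Week 60, that person is excluded.

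Nor can one say that the rate is understated overall. Missing follow-up lowers it, but pooling can raise Group A's figure above its drug-free risk.

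**Conclusion.** The concern holds in two respects that follow from the SAP text and the design. Converters without later cultures are counted as reversion-free, and on-drug time is pooled with drug-free time that only Group A has. The rate therefore does not estimate recurrence after completion of treatment, and no other planned analysis isolates that quantity.

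The sizes are illustrations. The 18.5-26.3% against 14.3% rests on assumed per-culture risks and conversion timing, and the 14-18% against 20% on an assumed unobserved share. Drug-free here means off dosing: Protocol 2.2 reports bedaquiline concentrations only about 40% lower four weeks after stopping.

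The arms have unequal opportunity to revert, but the direction is unknown. The endpoint is exploratory, descriptive and untested, so the primary conclusion is unaffected. This is a low-priority, inexpensive improvement.

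**What to change.** In SAP 5.5.2:

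- Start the risk period at the third qualifying negative culture.
- Restrict the denominator to converters with at least one later culture, and report by arm how many converters have none.
- Report on-treatment reversion by arm.
- Report Group A drug-free recurrence separately: the proportion with a positive culture at Weeks 52-60 among those who entered follow-up and have at least one follow-up culture.

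A Kaplan-Meier display of time to first positive, censored at last culture, is optional.

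The cost is a change of SAP wording and one extra table, from cultures already scheduled and a follow-up phase already defined in SAP 5.1. Intervals will be wide, with about 19 (Group A) and 6 (Group B) Week 24 converters expected under the planning rates.

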## 5.6. Safety Analyses

Safety and tolerability will be evaluated throughout the study from signing of the ICF onwards until the last study-related activity (end of study/early withdrawal).

All safety analyses will be based on the safety analysis set based on actual intervention received, unless otherwise specified. All summaries will be descriptive, and no inferential methods will be used to compare intervention arms for safety.

Safety and tolerability will be assessed by evaluating treatment emergent-adverse events (TEAEs), ECGs, physical examinations, vital signs measurements, clinical laboratory tests, pregnancy testing, and management of common expected toxicities.

For all continuous safety variables, descriptive statistics by intervention group will include the N, mean, standard deviation, median, minimum, and maximum. Categorical variables will be summarized by intervention group using frequency counts and percentages.

### 5.6.1. Extent of Exposure

The number and percentage of participants who receive each study intervention will be summarized.

Descriptive statistics of each study intervention (N, mean, SD, median, and range [minimum, maximum]) will be summarized for total duration, total number of treatment and total dose.

The number (%) of participants with a switch to individualized treatment regimen will be summarized by intervention group under investigation phase and optional investigation phase. .

Study intervention duration (weeks) is defined as (date of last dose of study intervention – date of first dose of study intervention +1) / 7.

Study intervention compliance will be summarized descriptively. See [Appendix 7](#) for further details.

### 5.6.2. Adverse Events

The verbatim terms used in the CRF by investigators to identify adverse events will be coded using the Medical Dictionary for Regulatory Activities (MedDRA version 27.1). Any AE occurring at or after the initial administration of study intervention through the end date of investigation phase defined in Section 5.1 is considered to be treatment emergent. If the event occurs on the day of the initial administration of study intervention, and either event time or time of administration are missing, then the event will be assumed to be treatment emergent. If the event date is recorded as partial or completely missing, then the event will be considered to be treatment emergent unless it is known to be prior to the first administration of study intervention based on partial onset date or resolution date. All reported treatment-emergent adverse events (TEAE) will be included in the analysis of investigation phase and optional investigation phase. All reported adverse events will be included in the analysis of follow-up phase. For each adverse event, the number and percentage of participants who experience at least 1 occurrence of the given event will be summarized by intervention group and analysis phase.

Summary tables will be provided for treatment-emergent adverse events, all adverse events will be presented in a descending order by incidence based on all participants (Total column):

- AEs
- Serious AEs (SAEs)
- AEs leading to discontinuation of study intervention
- AEs by severity
- AEs by relationship to study intervention
- AEs leading to dose interruption/dose modification of the study intervention
- AEs by onset time (at 3-months interval)

In addition to the summary tables, listings will be provided for participants who:

- Had SAEs
- Had AEs leading to discontinuation of study intervention/termination of study participation

Incidence of other treatment-emergent adverse events of special interest will be summarized by intervention group and analysis phase. See [Appendix 8](#) for list of adverse events in each category.

Deaths will be displayed by actual intervention received. Frequencies for the following parameters will be included in the summary table:

- Number of participants who died
- Cause of death
- Relationship to study intervention (yes/no)

A listing of participants who died will be provided.

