#### **8.3.1. Time Period and Frequency for Collecting Adverse Event and Serious Adverse Event Information**

##### **All Adverse Events**

All AEs and special reporting situations, whether serious or nonserious, will be reported from the time a signed and dated ICF is obtained until completion of the participant's last study-related procedure, which may include contact for follow-up of safety.

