#### **Adverse Events**

The verbatim terms used in the eCRF by investigators to identify AEs will be coded using the Medical Dictionary for Regulatory Activities (MedDRA). Treatment-emergent AEs are AEs with onset during the treatment period or that are a consequence of a preexisting condition that has worsened since baseline. All reported treatment-emergent AEs will be included in the analysis. For each AE, the percentage of participants who experience at least 1 occurrence of the given event will be summarized by treatment group. In addition, comparisons between treatment groups will be provided if appropriate.

Summaries, listings, datasets, or participant narratives may be provided, as appropriate, for those participants who die, who discontinue study intervention due to an AE, or who experience a severe AE of at least Grade 3 or an SAE.

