## **10.4. Appendix 4: Adverse Events, Serious Adverse Events, Product Quality Complaints, and Other Safety Reporting: Definitions and Procedures for Recording, Evaluating, Follow-up, and Reporting**

### **10.4.1. Adverse Event Definitions And Classifications**

#### **Adverse Event**

An AE is any untoward medical occurrence in a clinical study participant administered a pharmaceutical (investigational or noninvestigational) product. An AE does not necessarily have a causal relationship with the study intervention. An AE can therefore be any unfavorable and unintended sign (including an abnormal finding), symptom, or disease temporally associated with the use of a medicinal (investigational or noninvestigational) product, whether or not related to that medicinal (investigational or noninvestigational) product. (Definition per ICH)

This includes any occurrence that is new in onset or aggravated in severity or frequency from the baseline condition, or abnormal results of diagnostic procedures, including laboratory test abnormalities.

Note: The sponsor collects AEs starting with the signing of the ICF (refer to All Adverse Events under Section [8.3.1, Time Period and Frequency for Collecting Adverse Event and Serious Adverse Event Information](#), for time of last adverse event recording).

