#### **10.4.5. Procedures**

##### **All Adverse Events**

All AEs, regardless of seriousness, severity, or presumed relationship to study intervention, must be recorded using medical terminology in the source document and the eCRF. Whenever possible, diagnoses should be given when signs and symptoms are due to a common etiology (eg, cough, runny nose, sneezing, sore throat, and head congestion should be reported as "upper respiratory infection"). Investigators must record in the eCRF their opinion concerning the relationship of the AE to study therapy. All measures required for AE management must be recorded in the source document and reported according to sponsor instructions. If any change in seriousness or severity of a recorded AE is observed, the investigators must record it as new event in the eCRF.

For all studies with an outpatient phase, including open-label studies, the participant must be provided with a "wallet (study) card" and instructed to carry this card with them for the duration of the study indicating the following:

- Study number
- Statement, in the local language(s), that the participant is participating in a clinical study
- Investigator's name and 24-hour contact telephone number
- Local sponsor's name and 24-hour contact telephone number (for medical personnel only)

- Site number
- Participant number
- Any other information that is required to do an emergency breaking of the blind

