## Analysis Phase

Analysis phase	Start date	End date
Screening	The date of signing the informed consent	1 day before the first study intervention intake
Investigation	Date of the first study intervention intake	If the participants are from Group A, Min [Week 48, study discontinuation]
		If the participants from Group B will not convert to the optional cohort, Min [Week 60, study discontinuation]
		If the participants will convert to the optional cohort, 1 day before the optional investigation phase
Optional investigation	Date of the first BDQ+CAM+EB intake for nonconverters came from Group B	For nonconverters came from Group B, Min [Optional Week 48, study discontinuation]
Follow-up	If the participants are in Group A and moved to follow-up period, end of the investigation phase + 1 day	Min [Week 60, study discontinuation]

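### SAP 5.6.2 classes adverse events as treatment-emergent by date alone, so a record marking an improvement can count as a TEAE, and the stated window leaves the optional phase without a rule

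*SAP*

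**What the plan says.** **Recording.** Under Protocol 8.3.1, AEs "will be reported from the time a signed and dated ICF is obtained". Screening may take up to 10 weeks, extendable to 15 (Protocol 1.3, footnote a), so AEs that began before dosing will be on the eCRF. Protocol 10.4.5 then instructs: "If any change in seriousness or severity of a recorded AE is observed, the investigators must record it as new event in the eCRF". It gives no direction, so a fall in grade qualifies as well as a rise. The general AE definition in Protocol 10.4.1 is narrower: "This includes any occurrence that is new in onset or aggravated in severity or frequency from the baseline condition".

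**Classification.** Protocol 9.4.6 has two limbs: "Treatment-emergent AEs are AEs with onset during the treatment period or that are a consequence of a preexisting condition that has worsened since baseline". SAP 5.6.2 uses a date window instead. Treatment-emergent means "Any AE occurring at or after the initial administration of study intervention through the end date of investigation phase defined in Section 5.1". The section has no rule for joining successive records of one AE and no comparison with the grade before dosing. SAP Appendix 2, which lists departures from the protocol's analyses, mentions only the dropped per-protocol set.

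**Phases.** SAP 5.1 sets the end of the investigation phase. For Group B switchers it reads: "If the participants will convert to the optional cohort, 1 day before the optional investigation phase". SAP 5.6.2 nevertheless places TEAEs in the analysis of both the investigation and the optional investigation phase. It counts participants with at least one occurrence, by group and phase, and plans a table by time of onset in 3-month intervals.

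**A contrast within the SAP.** For laboratory toxicity grades, SAP 5.6.3.1 calls a value treatment-emergent only when it is worse than baseline.

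**The concern.** Two rules that are each workable give a wrong answer together. The recording rule creates a fresh record when an AE eases. The classification rule looks only at the date of that record. A participant who got better on treatment can then be tabulated as having a new event on treatment, just like one who got worse. The onset-time table has the same weakness, because a grade change in a later interval looks like a new onset.

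The optional cohort raises a separate problem. The window as written stops before that phase begins, yet the same section needs TEAEs for it. Whoever programs the tables must invent a rule.

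Safety and tolerability are a listed secondary endpoint (Protocol 3, SAP 1.1). The protocol also commits to evaluating safety in the optional cohort (note 1 to the objectives and endpoints). At stake is whether the TEAE and onset-time tables mean what their titles say.

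**Working it through.** The plan states no figure on this point to reproduce, so the check applies the written rules to simple cases.

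**Step 1. Inputs.** The recording rule is from Protocol 10.4.5, the TEAE window from SAP 5.6.2, and the phase ends from SAP 5.1. In Group A the investigation phase runs to Week 48 (target Day 337, SAP Table 2) or study discontinuation. For a switcher, take the optional phase to start on Day 225 for illustration (the Week 32 target day), so the investigation phase ends on Day 224. Assumption: the new record carries the date of the grade change.

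**Step 2. Rule.** An AE record is treatment-emergent if Day 1 ≤ record date ≤ end of investigation phase.

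| Case | Record date | Phase end | TEAE as written? | Sensible answer |
|---|---|---|---|---|
| Pre-dose Grade 2 falls to Grade 1, Group A | Day 10 | Day 337 | Yes | No |
| Pre-dose Grade 1 rises to Grade 2, Group A | Day 10 | Day 337 | Yes | Yes |
| Pre-dose AE, no change | before Day 1 | Day 337 | No | No |
| Rifamycin-period Grade 2 falls to Grade 1 after optional Day 1 | Day 230 | Day 224 | No | No |

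The first two rows get the same answer although one participant improved and the other worsened. The same holds in Group B with its own phase end. The last row gets the right answer only because the window excludes every optional-phase record, including a genuinely new AE on bedaquiline. If the date rule is restarted from optional Day 1 to fill the gap, that row becomes a TEAE of the optional phase.

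**Step 3. The other dating convention.** Suppose the new record keeps the original onset date. Improving pre-dose AEs are then no longer counted. But a pre-dose AE that truly worsens on treatment is not counted either, contrary to the second limb of Protocol 9.4.6. Neither convention works without a linking and grade rule.

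**Step 4. Onset-time table.** An AE that starts in the first 3-month interval and changes grade in the second has two dated records. With no linking rule, it can be shown as an onset in both.

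**Step 5. Size.** The documents give no AE rates and no frequency of grade changes. Incidence counts participants, so a false record adds to a term only when that participant has no other record of it in the phase. With the planned 62 per arm, the addition to a term is 100 × k/62 for k such participants:

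- k = 1: 1.6 percentage points
- k = 3: 4.8 percentage points
- k = 6: 9.7 percentage points

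These values of k are illustrations, not estimates.

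**The case against.** **What stands against the point.**

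- The dating convention is not in the protocol or SAP. The eCRF completion guidelines may settle it, and they are not available here. The AE definition in Protocol 10.4.1 also fits poorly with treating an improvement as a new AE. This makes the false-TEAE result conditional, but Step 3 shows that the other convention also fails.
- SAP 5.6 makes safety summaries descriptive, without inference between arms. The rules are the same in both randomised arms, and the primary endpoint is untouched.
- Participant-level counting limits the inflation. A grade change within one phase does not raise incidence for an AE already counted there.

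**Stronger readings that a reader might infer, and why they fail.**

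- *That the text inflates bedaquiline TEAEs in the optional cohort.* The written window excludes that phase. Inflation arises only if someone restarts the date rule. The defect in the text is a missing definition.
- *That the SAP removed a filter against improving AEs.* In Protocol 9.4.6 the worsening condition is an alternative limb that widens the definition. Restoring it alone would exclude nothing, because a record dated on treatment could still meet the first limb.
- *That false records are attributed to bedaquiline.* A phase table shows timing. The investigator assesses causality (Protocol 10.4.2), and SAP 5.6.2 tabulates relationship separately.
- *That TEAE tables are the only safety summary for the optional cohort.* Laboratory, vital-sign and ECG summaries are also by phase (SAP 5.6.3.1 to 5.6.3.3).
- *That the error is larger in Group A, because prior rifamycin is stopped before Day 1 and only Group B restarts it.* This is plausible, but no document gives a rate to support it.
- *That multiplying assumed rates of ongoing and improving AEs measures the inflation.* It mixes shares of participants with shares of AEs and ignores participant-level counting.

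**Conclusion.** The point holds as a gap in the SAP's TEAE rule, in two parts.

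First, with records dated at the change, which is the natural reading but an assumption, a screening-period AE that improves after first dose counts as a TEAE in either arm. Likewise, one continuous AE can be shown as an onset in more than one interval.

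Second, and without any dating assumption, the stated window contradicts the call for TEAEs in the optional phase.

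The total size cannot be derived from the documents. No hypothesis test depends on it. The gap is worth closing because the tables would otherwise rest on an unstated programming choice.

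**What to change.** In SAP 5.6.2:

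1. Link records that arise from a change in severity to the parent AE.
2. Define a TEAE separately for each phase. It is an AE that first starts on or after that phase's first dose, or one whose grade rises above the grade held just before that dose. A fall in grade creates neither a TEAE nor an onset.
3. For the onset-time table, date a new AE from its first record and a worsened pre-existing AE from the date of worsening.
4. End the window at the end of the corresponding phase, investigation or optional investigation.

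Reconcile the recording rule in Protocol 10.4.5 with the AE definition in 10.4.1 and the TEAE definition in 9.4.6, and state how a severity-change record is dated. List the TEAE definition in SAP Appendix 2.

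The cost is SAP and protocol wording, a linking step in the AE programming, and medical review of the few links that dates and terms do not settle. No new data are needed.
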